## 7.7 Data analysis

All analyses will be performed

A detailed statistical analysis plan (SAP) describing the planned analysis of the physician questionnaire and data presentation, including table shells, will be developed. The SAP will be finalized prior to database close. Any changes to the SAP will be captured in the final study report as changes to the SAP.

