#### Study design

This is a multinational, non-interventional, cross-sectional survey conducted among HCPs based in the EU/EEA who prescribe Piqray. The survey will assess the knowledge of HCPs prescribing Piqray in relation to the management of hyperglycemia in patients treated with Piqray. The survey will endeavor to collect a minimum to 30-50 completed surveys.

The survey will be conducted in 4 to 8 countries from the EU/EEA. These countries may include Austria, Luxembourg, Norway, Slovenia, Sweden, and the Netherlands plus up to 2 additional countries depending on timing and approval of commercialization of Piqray in additional EU/EEA countries. A sample of HCPs who may/do prescribe Piqray will be recruited from the target population of HCPs who manage care for patients with locally advanced or MBC.

A web-based survey approach will be used to collect data in all selected countries. Information collected will include receipt and reading of the Piqray educational material, and knowledge of key messages included in the Piqray educational materials.

Recruitment will take place a minimum of 6 months following the reimbursement and launch (availability on the market) of Piqray in each participating country.

The survey is anticipated to be open for a minimum of 3 months in each country. Follow-up reminders will be sent to non-respondents to support achieving the target sample size and reducing the impact of selection bias.

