#### Milestones

Planned dates of study milestones:

Start date of data collection: October 2021

Last date of data collection: October 2022

Submission of final report of study results: 30 April 2023

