#### 7.3.1 **Outcomes/endpoint variables**

Primary endpoint:

- Levels of knowledge of the risk for hyperglycemia, and risk factors for hyperglycemia, (survey question 4A, 6),
- Levels of knowledge of signs and symptoms of hyperglycemia (survey questions 5A-C), •
- Levels of knowledge of recommendations for monitoring for hyperglycemia prior to, and during, treatment with Pigray (survey questions 8A-C, 10, 15) and
- Levels of knowledge of recommendations for managing hyperglycemia during treatment ٠ with Piqray (survey questions 12-14).

The primary endpoint is a composite endpoint that combines correct responses given by HCPs to questions included in the composite. Specifically, the primary endpoint is a weighted composite knowledge score aggregated across the following survey questions: 4A, 5A-C, 6, 8A-C. 10, and 12-15. It is calculated as the number of all correctly answered questions divided by the number of all answered questions (i.e. questions that were answered either correct and not correct – unanswered questions are excluded).

Success criteria on the primary endpoint is defined as a weighted composite knowledge level of at least 70% across these key questions.

Secondary endpoint questions:

- Levels of reported receipt and reading of the Pigray Prescriber's/HCP Guide for • hyperglycemia, assessed as the percentages of HCPs who report receipt and reading of the same (survey questions 1, 2)
- HCPs' knowledge levels for each survey question regarding knowledge of, and • management of, hyperglycemia, assessed as the percentages of HCPs with correct responses to each question (individual responses to survey questions 4-15)
- The distribution of responses regarding the primary source from which HCPs learned • about the messages included in the Piqray Prescriber's/HCP Guide for Hyperglycemia, assessed as the percentages of HCPs who report using each of the possible sources as the primary source they used (survey question 3).

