## 7.6 Data management

Survey data collection will be completed on-line in Confirmit, a software platform specifically designed for the creation and delivery of multi-lingual surveys. Data collected will be stored at secure servers and will be maintained to ensure compliance with applicable local and national regulations.

Response sets for multiple-choice questions will be randomised to minimize bias. To minimize likelihood that respondents would look up answers and/or discuss the survey while taking it, respondents will be asked to complete survey in one sitting and will not be allowed to revise their answers after they advance to the next question.

Survey database lock is anticipated to occur shortly after the survey is closed in the last country. To reduce opportunity for bias, survey respondents will not be contacted to clarify or revise their responses to knowledge assessment-related questions.

Data management will be in accordance with the standard operating procedures (SOPs).

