#### Planned analyses

Survey administrative details (e.g., the number of invited HCPs, the number and percentage of responding HCPs, the number and percentage of eligible vs. ineligible HCPs, and the number and percentage of HCPs with partially vs. fully completed surveys) and analysis sets will be described overall and by country.

Confidential

Respondent characteristics/covariates will be summarized overall and by country.

Frequencies, percentages, and corresponding 95% 2-sided CI will be used to summarize the primary and secondary endpoints overall and by country. Depending on the final distribution of data within each subgroup, subgroup analyses of primary endpoints may also be analyzed by specialty and experience with Piqray.

For the primary endpoint, the point estimate of the weighted average composite percentage of HCPs who provide correct responses to the key question set will be estimated and assessed against the 70% threshold. Where subgroup analyses have small sample sizes (e.g., less than about 30), the results should be handled with caution. Although the 70% threshold is considered success, the associated confidence intervals for small subgroups will be wide, reflecting imprecision.

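### Section 7.7 lets the SAP be finalised up to about a year after unmasked answers start arriving, while parts of the scoring behind the 70% verdict are still open

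*Protocol*

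**What the plan says.** Protocol section 7.7 announces a detailed SAP and gives its only deadline: "The SAP will be finalized prior to database close". Later changes to it are to be reported in the final study report. Section 7.6 places the lock at the very end: "Survey database lock is anticipated to occur shortly after the survey is closed in the last country". The milestones in the abstract read "Start date of data collection: October 2021" and "Last date of data collection: October 2022"; Table 4-1 gives the end as 31 October 2022. Under section 7.1 countries enter at different times, and each stays open for at least three months.

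The abstract describes the design thus: "This is a multinational, non-interventional, cross-sectional survey conducted among HCPs based in the EU/EEA who prescribe Piqray". There is no comparison group, and nothing states that answers are withheld from those who write the SAP.

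The primary criterion is in section 7.3.1: "Success criteria on the primary endpoint is defined as a weighted composite knowledge level of at least 70% across these key questions". Section 7.7.2 applies it to the point estimate, which "will be estimated and assessed against the 70% threshold".

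On scoring, section 7.3.1 names the questions and defines the score as correctly answered questions over all answered questions, leaving out unanswered ones. Section 7.7.1 admits every HCP who completed at least one endpoint question, and section 7.7.2 rules out imputation.

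**The concern.** Finalising a SAP before lock is a sound safeguard where treatment allocation is masked, because the comparison cannot be seen until then. Here there is nothing to unmask. Whoever holds the accumulating answers could compute the score at any time, and the verdict depends on which side of 70% one percentage falls.

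The deadline would matter little if the scoring were fully fixed. Three parts are not.

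- **Items.** Section 7.3.1 takes only 5A-C from question 5. Table 7-1 also labels 5F, 5G and 5H as key, and so does the questionnaire in Appendix 13.1.
- **'I don't know/am not sure'.** Section 7.7.1 counts it in the denominator of each single question. Section 7.3.1 describes answered questions as correct or not correct and does not say where this response falls in the composite.
- **'Weighted'.** Sections 7.3.1 and 7.7.2 use the word, but no weights are given.

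The SAP has to resolve these. If it does so late, a reader of the report cannot be sure that the resolution was independent of the results.

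**Working it through.** **1. Length of the window.** From 1 October 2021 to 31 October 2022 is 395 days; from 31 October 2021 it is 365 days. Lock follows shortly after. A SAP signed in October 2022 would comply with section 7.7, although the earliest countries could have answered about a year before. Because launches are staggered, only the early countries' answers would be that old.

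**2. The plan's own precision figure.** Clopper-Pearson 95% limits at 70% correct are 50.6-85.3 for n=30 and 55.4-82.1 for n=50. The half-widths are (85.3 - 50.6)/2 = 17.35 and (82.1 - 55.4)/2 = 13.35. These match the 17.4 and 13.4 in Table 7-4 up to rounding. A result near the threshold is therefore plausible over a wide range of true knowledge.

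**3. Count of items.** Section 7.3.1: 4A (1), 5A-C (3), 6 (1), 8A-C (3), 10 (1), 12-15 (4), total 13. Table 7-1 marks the same 13 as key plus 5F, 5G and 5H, total 16.

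**4. Effect of the item list on one set of answers.** Assume 85% correct on tick-box items and 50% on the other six (6, 10, 12-15).

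- 13 items: (7 × 0.85 + 6 × 0.50)/13 = 8.95/13 = 68.8%, a fail.
- 16 items: (10 × 0.85 + 6 × 0.50)/16 = 11.50/16 = 71.9%, a pass.

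The effect can go the other way. If the 13 items score 75% and 5F-H score q, the 16-item score is (13 × 0.75 + 3q)/16. It falls below 70% once q is below (11.2 - 9.75)/3 = 48%.

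**5. Effect of the item list on the chance of a pass.** Simulation with these assumptions: n=40, average true knowledge 68% on every item, HCP random effect with SD 0.6 on the logit scale, and a score of exactly 70% counted as a pass.

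| Scoring | Chance of a pass |
|---|---|
| 13 or 16 items, fixed in advance | about 24-26% |
| Better of the two, chosen afterwards | about 28-29% |

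The gain is about 3 to 5 percentage points.

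**6. Effect of the 'I don't know' rule.** Let c be the share correct and d the share 'don't know' among all responses. The score is c if they count as answered and c/(1 - d) if they do not. With c = 65% and d = 10% (assumed), that is 65.0% against 0.65/0.90 = 72.2%. The share that moves a fail up to 70% is d = 1 - c/0.70:

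- c = 65%: 7.1%
- c = 67%: 4.3%
- c = 69%: 1.4%

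**7. 'Weighted'.** The pooled ratio equals the average of the per-question percentages, each weighted by the number who answered that question. The word may mean no more than this, but the protocol does not say so.

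**The case against.** The strongest reply is that the score is already in a protocol dated 8 June 2021, before collection starts. Item list, formula, treatment of unanswered questions, analysis set and threshold are all stated. This largely stands. A reader might infer that the whole weighting is still free, for example equal weight per domain or per numbered question, or that partial surveys could be counted in several ways. The documents do not support that. Such weightings would contradict the section 7.3.1 formula and be visible departures from it, and partial surveys are covered by sections 7.3.1, 7.7.1 and 7.7.2.

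A reader might also infer that the sponsor intends to look at the answers, or that a regulator could not detect a changed score. Neither follows. The monitoring metrics given as examples in section 7.4 are counts, the ENCePP checklist marks interim reports as not applicable, and the SAP deadline is only a latest date. The reported score can be compared with section 7.3.1. Per-question results are a secondary endpoint, so both item lists could be recomputed if numerators and denominators are given. That would show how far the verdict depends on the list. It would not show which list was planned, because the protocol supports both. The duty to report SAP changes does not cover choices made while the SAP is still a draft.

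Finally, the analysis is called descriptive, and sampling error exceeds the scoring effect. Both are true. However, section 7.3.1 still sets a pass/fail criterion on the point estimate, and a late choice of scoring is a bias that the confidence interval does not reflect.

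**Conclusion.** The point holds in limited form. The section 7.7 deadline does not protect an unmasked one-group survey, and three scoring matters remain that could be settled with answers in view: 5F-H, 'I don't know', and the meaning of 'weighted'. It is a gap in the safeguards, not evidence of a planned practice.

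The inflation from the item list alone is modest, about 3 to 5 points in the chance of a pass. That rests on the assumed n=40, 68% true knowledge and SD 0.6. The 'I don't know' rule can move the score further: by 7.2 points at the assumed 65% correct and 10% 'don't know'. The natural reading, by analogy with section 7.7.1, is that such a response counts as answered and not correct, but the composite definition does not say so. The answer levels used in steps 4 and 6 are illustrations, not forecasts. The change is worth making because it is cheap and removes a doubt about the primary verdict.

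**What to change.** Replace the deadline in section 7.7 with:

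> The SAP, including the item list and scoring of the primary composite, will be finalised and dated before the first survey invitation is sent. Later changes are listed with date and reason. Until database lock only counts (invited, eligible, completed) are released to the study team.

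Also reconcile section 7.3.1, Table 7-1, section 7.7.1 and Appendix 13.1 on three matters: one list of key items, with 5F-H either in or out everywhere; one explicit rule for 'I don't know/am not sure' in the composite; and either a definition of 'weighted' or its removal. Once these are settled in the protocol, SAP timing has much less left to affect.

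The cost is that the SAP is written some months earlier, plus a few lines of protocol text. No added data are needed, and the sample size, Table 7-4 and the 70% threshold do not change.

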## 7.7.1 Analysis populations

The primary analysis set will include all HCPs who have completed at least one of the endpoint questions in the survey. Denominators used to calculate descriptive statistics for each survey question will reflect the number of respondents who completed that particular question including responses of "I don't know/am not sure".

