## 6.2 Secondary objectives

[figure not shown]
- Assess HCPs' reported levels of receipt, and reading, of the Piqray Prescriber's/HCP Guide for hyperglycemia
- Assess HCPs' knowledge levels for each survey question regarding knowledge of, and management of, hyperglycemia
- Assess the primary source from which HCPs learned about the messages included in the Piqray Prescriber's/HCP Guide for hyperglycemia

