|  | Knowledge of what frequency should fasting glucose
be monitored when hyperglycemia occurs and
patients are treated with antihyperglycemic
medications (key question)   | Checked "weekly for at
least 8 weeks, followed
by once every 2 weeks,
and consider
consultation with a
healthcare professional
with expertise in the
treatment of
hyperglycemia" to
question 15 |
| HCPs' knowledge of
recommendations for
managing hyperglycemia
during treatment with
Piqray | Knowledge that for fasting glucose values that are
≤250 mg/dL (≤13.9 mmol/L), no Piqray dose
adjustment is required, and it is recommended to
manage by initiating or intensifying oral
antihyperglycemic treatment (key question)                  | Checked "true" to
question 12   |
|  | Knowledge of which fasting glucose values require
Piqray dosing to be interrupted (key question)   | Checked "any fasting
glucose value >250
mg/dL (>13.9 mmol/L) to
question 13   |
|  | Knowledge that "if Piqray dosing is interrupted due
to elevations in fasting glucose >250 mg/dL (>13.9
mmol/L), and fasting glucose decreases to <160
mg/dL (<8.9 mmol/L) within 3-5 days under
appropriate antihyperglycemia treatment, Piqray can | Checked "false" to
question 14  |

| Study objective domains assessed   | Corresponding variable (original data collected;
all are categorical variables)  | Operational
definition/derivation
"Calculated as the
percentage of HCPs
who" |  |
|--|---|--|--|
|  | be resumed at the starting dose level of 300 mg/day" is not accurate (key question)   |  |  |
| Assess whether HCPs received and read the  | Received the Guide for HCPs   | Checked "Yes" to
question 1   |  |
| Piqray Prescriber's/HCP
Guide for Hyperglycemia   | Read the Guide for HCPs   | Checked "Yes, all of it" +
"Yes, some of it" to
question 2                         |  |
| Primary source of the
indication, precautions for
use, and potential risks for
Piqray | Response choices: Piqray SmPC, Piqray Guide for
HCPs , NCA website, Professional society or
congress, Piqray product website, EMA website,
Clinical practice guidelines, Novartis representative,
Other | Checked each of the response choices to question 3                                       |  |

Note: Please see Appendix 13.1 for a full list of survey questions

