#### [END SURVEY SCREENING QUESTIONS]

#### MAIN SURVEY

[Preamble 1]: These questions are about important product information for Piqray. Please be sure to review all response choices for each question before answering each question.

1. Did you receive the "Piqray Prescriber's/HCP **Guide for Hyperglycemia**" that reminds healthcare professionals about certain how to identify, and manage, hyperglycemia in patients treated with Piqray?

```
🗆 Yes
```

#### □ No → PROCEED TO QUESTION 3

- □ I don't know/am not sure → PROCEED TO QUESTION 3
- 2. Did you read or review the "Piqray Prescriber's/HCP Guide for Hyperglycemia"?
  - Yes, all of it
    Yes, some of it
    No
    I don't know/am not sure
- What is the primary source you use to learn about the indication, precautions for use, and potential risks for Piqray? (please tick only 1 response)

D Piqray Summary of Product Characteristics

- D Piqray Prescriber's/HCP Guide for Hyperglycemia
- National Competent Authority website
- Professional Society or Congress
- □ The Piqray product website
- The European Medicines Agency website
- Clinical practice guidelines
- A representative from Novartis
- □ Other (not listed above)
- □ I do not know/am not sure

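### Two secondary endpoints are not measured as defined: the reading rate covers only HCPs who report receiving the Guide, and Question 3 does not ask where the Guide's hyperglycemia messages were learned

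*Protocol*

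**What the plan says.** **Reading of the Guide.** Section 7.3.1 makes receipt and reading a secondary endpoint, "assessed as the percentages of HCPs who report receipt and reading of the same", from survey questions 1 and 2. Table 7-1 has a row "Read the Guide for HCPs" that counts the two affirmative answers to Question 2, under a column header that makes every entry a percentage of HCPs. The comment to section 3 of the ENCePP checklist (Annex 2) describes receipt and reading as proportions of respondents.

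In Appendix 13.1, two of the three answers to Question 1 bypass Question 2: "No → PROCEED TO QUESTION 3" and "I don't know/am not sure → PROCEED TO QUESTION 3". Section 7.7.1 then sets the base: "Denominators used to calculate descriptive statistics for each survey question will reflect the number of respondents who completed that particular question", with don't-know answers included.

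**Primary source.** Section 6.2 states the third secondary objective: "Assess the primary source from which HCPs learned about the messages included in the Piqray Prescriber's/HCP Guide for hyperglycemia". The Abstract and section 7.3.1 word it the same way, and section 7.3.1 assigns Question 3 alone to it. Question 3 reads: "What is the primary source you use to learn about the indication, precautions for use, and potential risks for Piqray". The matching row of Table 7-1 follows the wording of Question 3, not that of section 7.3.1.

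**The concern.** For reading, the skip and the denominator rule act together. Anyone who did not receive the Guide, or is unsure, leaves the base of the reading percentage. The figure then describes how many self-reported receivers read the Guide, under a label that promises a percentage of HCPs. It need not move when dissemination fails, although confirming receipt is part of the study's stated objective.

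For source, the item and the objective differ in subject. The Guide deals with hyperglycemia only, while Question 3 covers the indication, precautions and risks of the product. An HCP can truthfully name the SmPC in answer to Question 3 and still have learned hyperglycemia management from the Guide. The comment to section 7 of the ENCePP checklist names this source assessment as the way confounding is addressed, so the mismatch also weakens any attempt to attribute knowledge to the Guide.

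**Working it through.** The protocol states no reading rate or receipt rate, so there is no figure of its own to reproduce. The check is on definitions, followed by arithmetic under assumed rates.

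**(a) Reading rate**

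Inputs from the protocol:
- Question 2 is seen only by those who answer yes to Question 1 (Appendix 13.1).
- The denominator is those who completed the question (7.7.1).
- The planned minimum is 30 to 50 completed surveys (7.1).
- Receiving the Guide is not a condition of taking part (ENCePP checklist, comment to section 5), and section 7.4 allows top-up outreach through internet research or professional societies. Receipt below 100% is therefore possible.

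Assumed: receipt of 40% to 100%, and 80% of receivers reading all or some of the Guide, with no blank Question 2.

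Let N be respondents to Question 1, R those who report receipt, and k those who report reading.
- Rate under 7.7.1 with the skip: k/R.
- Rate over respondents: k/N = (R/N) × (k/R).
- Ratio of the two: (k/R)/(k/N) = N/R = 1/(receipt rate).

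With N = 50 (exact 95% intervals in brackets where computed):

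| Assumed receipt | k/R | k/N | Factor |
|---|---|---|---|
| 100% | 40/50 = 80.0% (66.3–90.0) | 40/50 = 80.0% (66.3–90.0) | 1.00 |
| 80% | 32/40 = 80.0% (64.4–90.9) | 32/50 = 64.0% (49.2–77.1) | 1.25 |
| 60% | 24/30 = 80.0% (61.4–92.3) | 24/50 = 48.0% (33.7–62.6) | 1.67 |
| 50% | 20/25 = 80.0% | 20/50 = 40.0% | 2.00 |
| 40% | 16/20 = 80.0% (56.3–94.3) | 16/50 = 32.0% (19.5–46.7) | 2.50 |

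With N = 30 and 60% receipt, the figures are 14/18 = 77.8% (52.4–93.6) against 14/30 = 46.7% (28.3–65.7). The same interval method returns Table 7-4's limits at 70% knowledge: 50.6–85.3 for n = 30 and 55.4–82.1 for n = 50.

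The k/R column stays at 80% while receipt falls from 100% to 40%. Also, section 7.7.1 keeps don't-know answers in denominators, yet the skip removes HCPs who are unsure of receipt from the reading base.

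**(b) Primary source**

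No arithmetic applies. Side by side:

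| | Objective and endpoint (6.2, 7.3.1) | Question 3 and Table 7-1 row |
|---|---|---|
| Subject | the Guide's hyperglycemia messages | indication, precautions and risks of the product |
| Time, as put in 6.2 and in Question 3 | where the HCP learned them | what the HCP uses now |

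No other item asks for a source, so the answer that the objective needs is not collected.

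**The case against.** **The endpoint may not be one joint proportion.** Section 7.3.1 speaks of percentages in the plural, and Table 7-1 has separate rows for received and read. This stands: the protocol does not define a single received-and-read rate. But the read row, taken alone, is still headed as a percentage of HCPs, and the checklist says respondents. Neither restricts it to receivers.

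**The denominator may be left to the SAP.** Section 7.7 assigns table shells to the SAP, and section 7.7.2 allows a missing category where applicable. That leaves a little room. But section 7.7.1 fixes the per-question base in the protocol, and nothing says that HCPs skipped by design return to it. No SAP can repair the stem of Question 3 once answers are collected.

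**Dissemination failure would be hidden.** A reader might infer this, and the documents do not support it. Everyone is asked Question 1, receipt is reported in its own right, and section 7.7.2 requires frequencies as well as percentages. In the 50% example the report would show 25/50 received and 20/25 read, so 20/50 can be recovered. What remains is a reading rate with the wrong base for its label.

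**Low receipt is only assumed.** True. Invitees come mainly from the dissemination list (7.2, 7.9) and supplementary outreach is optional. At high receipt the factor is near 1.

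**Question 3 understates the Guide's role.** This too is tempting but not derivable. Question 3 follows directly on two questions that name the Guide, and it lists the Guide as an option, which could push answers the other way.

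**Counting unsure HCPs as non-readers would be imputation.** This is a fair caution about the remedy. It is met by defining the measure as the percentage who report reading, and by not recoding a blank Question 2 from someone who reported receipt.

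**Conclusion.** Both mismatches stand on the protocol's own text. The reading rate as fixed is a receivers-only figure that exceeds the all-respondent figure by 1/(receipt rate). That is 1.25 at 80% receipt and 2.0 at 50%; both receipt rates are assumptions, and the formula supposes that no receiver leaves Question 2 blank. At full receipt the two figures agree. A rate among receivers is a legitimate measure, but it is not labelled as one and is not what section 7.3.1, Table 7-1 and the checklist describe. Question 3 does not measure the third secondary objective; the size and direction of the resulting error cannot be stated.

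A reader might take this further and doubt the study's success criterion. That does not follow: the 70% threshold applies to the primary composite, which uses neither Questions 1 and 2 nor Question 3. The two endpoints are secondary, descriptive and without a threshold. The corrections are worth making because they are nearly free and change what those endpoints report.

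**What to change.** 1. In section 7.7.1 and the reading row of Table 7-1, define the measure as the percentage who report reading all or some of the Guide among all respondents who answered Question 1. Count no and don't know at Question 1 as not reporting reading. Show a blank Question 2 after yes at Question 1 as missing, not as not read.
2. Keep the rate among those reporting receipt as an additional line, labelled as such.
3. Before launch and translation, reword Question 3 and its Table 7-1 row to ask for the primary source from which the HCP learned about identifying and managing hyperglycemia with Piqray. The list of sources can stay. Rewording the objective to match Question 3 would also remove the contradiction, but the study would then no longer ask where the Guide's messages were learned.

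The cost is one denominator sentence, two table rows and one question stem. The number of questions and the burden on respondents do not change.
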